8.1.2 Nivolumab (NSC 748726)

Amino Acid Sequence: 4 polypeptide chains, which include 2 identical heavy chains with 440 amino acids and 2 identical light chains.

Other Names: BMS-936558, MDX1106

Classification: Anti-PD-1Mab

M.W.: 146,221 Daltons

Mode of Action: Nivolumab targets the programmed death-1 (PD-1, cluster of differentiation 279 [CD279]) cell surface membrane receptor. PD-1 is a negative regulatory receptor expressed by activated T and B lymphocytes. Binding of PD-1 to its ligands, programmed death-ligand 1 (PD-L1) and 2 (PD-L2), results in the down-regulation of lymphocyte activation. Nivolumab inhibits the binding of PD-1 to PD-L1 and PD-L2. Inhibition of the interaction between PD-1 and its ligands promotes immune responses and antigen-specific T-cell responses to both foreign antigens as well as self-antigens.

Description: Nivolumab Injection is a clear to opalescent, colorless to pale yellow liquid; light (few) particulates may be present. The drug product is a sterile, nonpyrogenic, single-use, isotonic aqueous solution formulated in sodium citrate, sodium chloride, mannitol, diethylenetriamine pentacetic acid (pentetic acid) and polysorbate 80 (Tween[®] 80), and water for injection. Dilute solutions of hydrochloric acid and/or sodium hydroxide may be used for pH adjustment (pH 5.5-6.5).

How Supplied: Nivolumab is supplied by Bristol-Myers Squibb and distributed by the Pharmaceutical Management Branch, CTEP/DCTD/NCI as 100 mg vials (10 mg/mL) with a 0.7 mL overfill. It is supplied in 10 mL type I flint glass vials, with fluoropolymer film-laminated rubber stoppers and aluminum seals.

Preparation: Nivolumab injection can be infused undiluted (10 mg/mL) or diluted with 0.9% Sodium Chloride Injection, USP or 5% Dextrose. When the dose is based on patient weight (i.e., mg/kg), nivolumab injection can be infused undiluted or diluted to protein concentrations as low as 0.35 mg/mL. When the dose is fixed (eg, 240 mg, 360 mg, or 480 mg flat dose), nivolumab injection can be infused undiluted or diluted so as not to exceed a total infusion volume of 160 mL. For patients weighing less than 40 kilograms (kg), the total volume of infusion must not exceed 4 mL per kg of patient weight. During drug product preparation and handling, vigorous mixing or shaking should be avoided.

Nivolumab infusions are compatible with polyvinyl chloride (PVC) or polyolefin containers and infusion sets, and glass bottles.

Storage: Vials of Nivolumab injection must be stored at 2°-8°C (36°-46°F) and protected from light and freezing. The unopened vials can be stored at room temperature (up to 25°C, 77°F) and room light for up to 48 hours.

If a storage temperature excursion is identified, promptly return Nivolumab to 2°C-8°C and quarantine the supplies. Provide a detailed report of the excursion (including documentation of temperature monitoring and duration of the excursion) to [contact] for determination of suitability.

Stability: Shelf-life surveillance of the intact vials is ongoing.

The administration of undiluted and diluted solutions of Nivolumab must be completed

within 24 hours of preparation. If not used immediately, the infusion solution may be stored up to 24 hours in a refrigerator at 2°-8°C (36°-46°F) and a maximum of 8 hours of the total 24 hours can be at room temperature (up to 25°C, 77°F) and room light. The maximum 8-hour period under room temperature and room light conditions includes the product administration period.

CAUTION: The single-use dosage form contains no antibacterial preservative or bacteriostatic agent. Therefore, it is advised that the product be discarded 8 hours after initial entry.

Route of Administration: Intravenous infusion over 30 minutes. Do not administer as an IV push or bolus injection.

Method of Administration: Administer through a 0.2 micron to 1.2 micron pore size, low-protein binding polyethersulfone membrane in-line filter.

Potential Drug Interactions: The indirect drug-drug interaction potential of nivolumab was assessed using systemic cytokine modulation data for cytokines known to modulate CYP enzymes. There were no meaningful changes in cytokines known to have indirect effects on CYP enzymes across all dose levels of nivolumab. This lack of cytokine modulation suggests that nivolumab has no or low potential for modulating CYP enzymes, thereby indicating a low risk of therapeutic protein-drug interaction.

Patient Care Implications: Women of childbearing potential (WOCBP) receiving nivolumab must continue contraception for a period of 5 months after the last dose of nivolumab. Men receiving nivolumab and who are sexually active with WOCBP must continue contraception for a period of 7 months after the last dose of nivolumab.

Availability

Nivolumab is an investigational agent supplied to investigators by the Division of Cancer Treatment and Diagnosis (DCTD), NCI.

Nivolumab is provided to the NCI under a Collaborative Agreement between the Pharmaceutical Collaborator and the DCTD, NCI (see Section 12.3).

8.1.3 Ipilimumab (NSC 732442)

Chemical Name or Amino Acid Sequence: 4 polypeptide chains, 2 identical heavy chains with 447 amino acids and 2 identical light chains consisting of 215 amino acids.

Other Names: Anti-CTLA-4 monoclonal antibody, MDX-010, Yervoy™

Classification: Human monoclonal antibody

M.W.: 147,991 Daltons

Mode of Action: Ipilimumab is specific for the CTLA4 antigen expressed on a subset of activated T-cells. CTLA4 interaction with the B7 molecule, one of its ligands expressed on professional antigen presenting cells, can down-regulate T-cell response. Ipilimumab is, thought to act by blocking the interaction of CTLA4 with the B7 ligand, resulting in a blockade of the inhibitory effect of T-cell activation. The CTLA4/B7 creates the interaction.

Description: Ipilimumab is a fully human immunoglobulin (IgG_{1κ}) with two manufacturing processes – ongoing trials have been using substances manufactured using Process B. New clinical trials will be using ipilimumab that is manufactured by Process C. The Process C has been developed using a higher producing sub-clone of the current Master Cell Bank, and modified cell culture and purification steps.

How Supplied: Bristol-Myers-Squibb (BMS) supplies Ipilimumab to the DCTD/NCI. Ipilimumab injection, 200 mg/40 mL (5 mg/mL), is formulated as a clear to slightly opalescent, colorless to pale yellow, sterile, nonpyrogenic, single-use, isotonic aqueous solution that may contain particles.

Each vial is a Type I flint glass vial with gray butyl stoppers and sealed with aluminum seals.

	Process C
Component	200 mg/ vial^a
Ipilimumab	213 mg
Sodium Chloride, USP	249 mg
TRIS-hydrochloride	134.3 mg
Diethylenetriamine pentacetic acid	1.67 mg
Mannitol, USP	426 mg
Polysorbate 80 (plant-derived)	4.69 mg
Sodium Hydroxide	QS to pH 7
Hydrochloric acid	QS to pH 7
Water for Injection	QS: 42.6 mL
Nitrogen ^b	Processing agent

^aIncludes 2.6 mL overfill.

^bNitrogen is used to transfer the bulk solution through the pre-filled and sterilizing filters into the aseptic area.

Preparation: Ipilimumab is given undiluted or further diluted in 0.9% NaCl Injection. Ipilimumab is stable in a polyvinyl chloride (PVC), non-PVC/non DEHP (di-(2-ethylhexyl) phthalate) IV bag or glass container up to 24 hours refrigerated at (2⁰ to 8⁰ C) or at room temperature/ room light.

Recommended safety measures for preparation and handling include protective clothing, gloves, and safety cabinets.

Storage: Store intact vials refrigerated at (2⁰ to 8⁰ C), protected from light. Do not freeze.

Stability: Shelf-life surveillance of the intact vials is ongoing. Solution as described above is stable up to 24 hours refrigerated at (2⁰ to 8⁰ C) or at room temperature/ room light.

CAUTION: Ipilimumab does not contain antibacterial preservatives. Use prepared IV solution immediately. Discard partially used vials.

Route(s) of Administration: Intravenous infusion. Do not administer ipilimumab as an IV push or bolus injection.

Method of Administration: Can use a volumetric pump to infuse ipilimumab at the protocol-specific dose(s) and rate(s) via a PVC IV infusion set with an in-line, sterile, non-pyrogenic, low-protein-binding filter (0.2 micron to 1.2 micron).

Patient Care Implications: Monitor patients for immune-related adverse events, e.g., rash/vitiligo, diarrhea/colitis, uveitis/episcleritis, hepatitis and hypothyroidism. If you suspect toxicity, refer to the protocol guidelines for ruling out other causes.

Availability

Ipilimumab is an investigational agent supplied to investigators by the Division of Cancer Treatment and Diagnosis (DCTD), NCI.

Ipilimumab is provided to the NCI under a Collaborative Agreement between the Pharmaceutical Collaborator and the DCTD, NCI (see Section 12.3).

8.1.4 Agent Ordering and Agent Accountability

- 8.1.4.1 NCI-supplied agents may be requested by the responsible investigator (or their authorized designee) at each participating institution. Pharmaceutical Management Branch (PMB) policy requires that agent be shipped directly to the institution where the patient is to be treated. PMB does not permit the transfer of agents between institutions (unless prior approval from PMB is obtained). The CTEP-assigned protocol number must be used for ordering all CTEP-supplied investigational agents. The responsible investigator at each participating institution must be registered with CTEP, DCTD through an annual submission of FDA Form 1572 (Statement of Investigator), Biosketch, Agent Shipment Form, and Financial Disclosure Form (FDF). If there are several participating investigators at one institution, CTEP-supplied investigational agents for the study should be ordered under the name of one lead investigator at that institution.

In general, sites may order initial agent supplies when a subject is being screened for enrollment onto the study.

Active CTEP-registered investigators and investigator-designated shipping designees

and ordering designees can submit agent requests through the PMB Online Agent Order Processing (OAOP) application. Access to OAOP requires the establishment of a CTEP Identity and Access Management (IAM) account and the maintenance of an “active” account status and a “current” password. For questions about drug orders, transfers, returns, or accountability, call or email PMB any time. Refer to the PMB’s website for specific policies and guidelines related to agent management.

8.1.4.2 Agent Inventory Records – The investigator, or a responsible party designated by the investigator, must maintain a careful record of the receipt, dispensing and final disposition of all agents received from the PMB using the appropriate NCI Investigational Agent (Drug) Accountability Record (DARF) available on the CTEP forms page. Store and maintain separate NCI Investigational Agent Accountability Records for each agent, strength, formulation and ordering investigator on this protocol.

8.2 Blinatumomab Administration-Inpatient and Outpatient Procedures

Inpatient

Blinatumomab will be administered as a continuous IV infusion over four weeks followed by a two-week treatment free interval. It is recommended that patients are hospitalized at least during the first 14 days of the first cycle and the first two days of each of the subsequent cycle. The hospitalization time depends on the investigator’s judgment, as well as the safety and tolerability of blinatumomab.

The infusion bags will be changed by site nursing personnel. Close monitoring during the first 48 - 72 hours of treatment in the first cycle will be indicated because of the potential AEs associated with T cell redistribution and potential cytokine release effects triggered by the administration of blinatumomab. Nurses/physicians trained in critical care medicine should be available for immediate intervention in case of complications. Afterwards the treatment may be continued on an outpatient basis, if it is judged to be safe and feasible by the investigator.

Outpatient

In the outpatient setting, several options are available for blinatumomab administration:

- The patient will return to the study site for all changes of infusion bags.
- If allowable by the treating physician's institution, infusion bag changes may be performed in the patient's home by an ambulatory/home care service provider. In this case, the ambulatory/home care service provider will be given the remaining bags for the week of treatment that have been prepared by the site investigational pharmacy in a validated shipper for transport. The validated shipper will maintain proper storage conditions during transport for the prepared infusion bags. The infusion bags are to be kept/stored at the ambulatory/home care service provider in a controlled temperature monitored refrigerator used at the ambulatory/home care service provider. Patients will be visited by an ambulatory/home care service provider at specific intervals to change the infusion bag. The ambulatory/home care service will be trained and will receive written instruction for transport of drug from the site investigational pharmacy and from the ambulatory/home care service provider to the patient's home for infusion. If necessary shipment of the infusion bags from the site investigational pharmacy to the ambulatory/home care service provider for subsequent transport to the patient's home for infusion will be allowed via use of a validated shipper and a traceable method of shipment via an express courier.
- If all options above are not feasible, shipping the prepared infusion bag in a pre-qualified insulated shipper directly to patient's home via overnight courier delivery service for administration by home healthcare agency staff is acceptable. **Patients are not to open the box upon the receipt of the drug.**

NOTE: The NCI Drug Accountability Record Form (DARF) must reflect all transaction for preparing and providing the infusion bags to an ambulatory/home care service provider. The ambulatory/home care service provider must also keep DARFs to log in/out date when receiving the infusion bags from the sites and when dispensing the infusion bags to patients as well as the times of all infusion bag changes.

NOTE: The pre-qualified shipper box will include a form of shipment of blinatumomab IV bag(s) to patient's home. That form will be completed by site/pharmacy prior to shipping the IV blinatumomab bags. The form is available as Appendix H. The home healthcare service will open the box at the time that the IV drug is to be administered to patient. The home healthcare service staff will complete the second portion of the form and any discrepancy must be reported immediately to the site pharmacy.

9. BIOMARKER, CORRELATIVE, AND SPECIAL STUDIES

9.1 Overview

Mandatory research bone marrow aspirates (40 cc-4 green top tubes-sodium heparin) and research peripheral blood specimens (preferred 100 cc [minimum 60 cc]-10 (min 6) green top tubes-sodium heparin) will be obtained (preferentially on the same day): at baseline (1-7 days prior to the initiation of study treatment; up to 14 days prior to the initiation of study treatment allowed for patients requiring prephase treatment), prior to first dose of nivolumab / ipilimumab in cycle 1 (day 8-11 +/- 4 days), at the end of cycles 1 and 2 (day 29-35), and every 3-4 months up to 1 yr, or at the time of relapse or off study.

Additional research peripheral blood specimens (preferred 40 cc [minimum 30 cc]- 3 or 4 green top tubes) will be collected in cycle 1 (days 1, 15, and 22; all ± 3 days), and prior to cycle 2 (day 40-42 of cycle 1).

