5. TREATMENT PLAN

5.1 Agent Administration

Treatment will be initiated on an inpatient basis. Reported adverse events and potential risks are described in Section 7. Appropriate dose modifications are described in Section 6. No investigational or commercial agents or therapies other than those described below may be administered with the intent to treat the patient's malignancy. The cycle length is 42 days for all dose levels.

Treatment will consist of the combination of blinatumomab and nivolumab, with or without ipilimumab per the dose escalation schedule below. A run-in of blinatumomab (10 days with planned dose escalation on day 8) prior to combination therapy will be incorporated at all dose levels to help determine the effect of blinatumomab on immune regulatory pathways in leukemia and as a means of minimizing the potential for overlapping toxicities, as many of blinatumomab's most significant side effects occur within the first few days of administration or after a dose increase. Nivolumab with or without ipilimumab will start on day 11 of cycle 1. When nivolumab and ipilimumab are scheduled on the same day, nivolumab should be given first followed by ipilimumab as described in Section 5.3.4

Pre-treatment phase (pre-phase): Pre-phase treatment with dexamethasone 10 mg/m² (maximum total 24 mg per day intravenously) for up to 5 days for patients with bone marrow blasts more than 50%, peripheral blood blasts of 15,000/ μ L or higher, or elevated lactate dehydrogenase suggesting rapidly progressing disease as per investigator's assessment is required unless other cytoreductive measures as outlined below have already been successfully implemented. Pre-phase treatment should be completed at least 24 hours before starting blinatumomab (study treatment). Other pre-phase treatment for cyto-reduction including cyclophosphamide, 6-MP, hydroxyurea, or corticosteroids (dexamethasone, prednisone or similar) (in patients not meeting the aforementioned criteria) may be used at the investigator's discretion but must be completed at least 24 hours prior to blinatumomab infusion.

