10. STUDY CALENDAR

Notations/reminders for all calendars:

- Baselines assessments are to be conducted within 7 days prior to start of protocol therapy unless otherwise noted. If the patient will receive pre-phase treatment, then a BM aspirate and biopsy within 14 days of starting treatment on this study is allowed.
- On study physical exams to include medical history since last assessment, as appropriate.
- Pregnancy test (serum or urine) is required for women of childbearing potential ≤ 3 days prior to study enrollment and must be negative to initiate treatment.
- Correlative blood and bone marrow sample participation is mandatory.
- Additional tests may be performed at the discretion of the treating investigator or site as per routine practice, or as otherwise clinically indicated.
- The schedule should be followed as closely as is realistically possible; however, the schedule may be modified due to problems such as scheduling delays or conflicts (e.g., clinic closure, poor weather conditions, vacations, etc.) with the guidance of the Protocol Chair/designee, as appropriate, and will not be reportable as a deviation unless the endpoints of the study are affected.

Table 10.1	Screening	Cycle 1			Cycles 2-5			Beyond Cycle 5		
Treatment Cycle:	Main Study Screening	Week1	Weeks 2-4	Weeks 5-6	Week 1	Weeks 2-4	Weeks 5-6	Every 2 weeks for up to 1 year	Every 3 months for 2 years after completing study treatment	Off Study
Blinatumomab (D 1-28 every 42 days)		X	X		X (D1-D28)	X (D1-D28 only)				
Nivolumab (every 2 weeks starting on D11 of Cycle 1) ¹			X	X		X	X	X		
Ipilimumab (every 6 weeks starting on D11 of Cycle 1) ¹			X			X		X (Every 6 weeks)		
Informed Consent	X									
Inclusion/Exclusion Criteria	X									
Demographics and Medical History	X									
Concurrent Meds	X	X-----X								
History/Physical Exam ²	X	X	X	X	X	X	X	X	X	X
Vital Signs including oxygen saturation ²	X	X	X	X	X	X	X	X	X	
Height/Weight ²	X	X			X			X (every 6 weeks)		
Performance Status ²	X	X			X			X (every 6 weeks)		
CBC with	X	X	X	X	X	X		X	X	X

Differential ³										
PT, aPTT, fibrinogen, D-dimer ⁴	X	X	X		X					
Serum chemistry ⁵	X	X	X	X	X	X	X	X	X	X
Amylase, lipase ⁶	X		X	X		X	X	X		
TSH (with reflective Free T3 and FreeT4) ⁶	X		X	X		X	X	X		
Hepatitis Serologies ⁷	X									
Quantitative Immunoglobulin ⁸	X				X ⁸ (cy 2 only)		X ⁸ (end of cy 5)	X ⁸ (every 3-6 months)	X ⁸ (every 3-6 months)	
Urinalysis	X									
Serum or urine HCG for WOCBP only ⁹	X				X			X (every 6 weeks)		

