13.8 Analysis of Exploratory Endpoints

13.8.1 Characterizing T cell populations

The analyses of pre- and post-treatment PB and BM specimens for immune parameters will be descriptive and graphical in nature. Data will be summarized for each patient group separately (blinatumomab plus nivolumab; blinatumomab plus nivolumab and ipilimumab). Flow values at each time point will be summarized using geometric means and standard deviation. Differences in baseline values between patient subgroups will be explored using linear regression models. We are specifically interested in determining what pretreatment signature is associated with outcome, such as having a complete response or becoming refractory. To this end, we will use logistic regression models with ROC analysis to describe which pretreatment parameters are potential predictors of outcomes following treatment. Values will be checked for skewness and log-transformed as appropriate. The change in flow values at each time point after blinatumomab and blinatumomab plus checkpoint inhibitor(s) relative to the baseline value will be modeled using mixed-effects, linear regression models that include fixed effects for time point and a random effect for the patient to account for within-patient correlation of measurements. Post-treatment changes in T cell populations will be correlated with clinical outcomes such as CR vs. No CR or MRD vs. No MRD using interaction tests. T cell subsets in the PB and BM defined by multicolor flow cytometry will be summarized before and after treatment with blinatumomab alone or plus checkpoint inhibitors by treatment group using summary statistics. Differences in T cells before and after treatment will be explored using non-parametric Wilcoxon signed rank tests or paired t tests as appropriate. The expression of co-inhibitory/-stimulatory molecules will also be examined in the same way.

13.8.2 Characterization of T cell transcriptional signature before and after treatment.

Expression levels will be summarized at pre-treatment and post-treatment using standard descriptive statistics. Differentially-expressed genes and corresponding fold-changes will be analyzed using standard statistics and through the use of Ingenuity pathway analysis as described previously. We will identify differentially-expressed genes by patient subgroups such as CR v. NR and MRD v. No MRD using interaction tests.

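### In patients given pre-phase cytoreduction the correlative baseline may precede it, so the change from baseline to day 8-11 mixes pre-phase and blinatumomab effects

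*Combined protocol and SAP*

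**What the plan says.** **Baseline sample.** Section 9.1 takes baseline marrow and blood 1-7 days before study treatment, preferably on the same day, with an extension: "up to 14 days prior to the initiation of study treatment allowed for patients requiring prephase treatment". The general notes to the Study Calendar (Section 10) repeat the extension for marrow: "If the patient will receive pre-phase treatment, then a BM aspirate and biopsy within 14 days of starting treatment on this study is allowed".

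**Pre-phase.** Section 5.1 describes "Pre-phase treatment with dexamethasone 10 mg/m² (maximum total 24 mg per day intravenously) for up to 5 days" in patients who meet blast or LDH criteria, unless other cytoreduction has already succeeded. It also allows, at the investigator's discretion in other patients, "Other pre-phase treatment for cyto-reduction including cyclophosphamide, 6-MP, hydroxyurea, or corticosteroids", with no stated maximum duration. On timing, "Pre-phase treatment should be completed at least 24 hours before starting blinatumomab".

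**Day 1 blood.** Section 9.1 schedules further research blood that "will be collected in cycle 1 (days 1, 15, and 22; all ± 3 days"). Calendar footnote 15 has the same window. The Appendix F worksheet gives cycle 1 day 1 a window of minus 3 days only, with 30-40 cc of blood and no marrow.

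**Analysis.** Under Section 13.8.1, the change in flow values at each time point "relative to the baseline value will be modeled using mixed-effects, linear regression models", with a fixed effect for time point and a random effect for patient. Appendix C repeats this, and Sections 13.8.3 and 13.8.4 reuse the model for blasts and cytokines. No pre-phase covariate, stratum, sensitivity analysis or alternative reference is given.

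**The concern.** Section 13.1 says the ten-day blinatumomab run-in is there to help show what blinatumomab does to immune parameters. The natural estimate is the change from baseline to the sample taken before the first checkpoint inhibitor dose (day 8-11). If a patient's baseline was drawn before dexamethasone, cyclophosphamide, 6-MP or hydroxyurea, that change has two causes. In a patient without pre-phase it does not. The same model coefficient then averages two different quantities.

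The mix is not random. Required pre-phase is triggered by tumour burden or suspected rapid progression. If burden is also related to response, the difference can feed into the comparisons of change by CR or MRD status. A patient random effect does not help: it handles correlation within a patient, not a systematic shift in the mean change of one group.

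**Working it through.** The plan states no power, sample size or effect figure for these analyses, so there is nothing of its own to reproduce. The check is a timeline, a decomposition and an illustration.

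**1. Can the baseline precede pre-phase?** Inputs from Section 5.1: up to 5 days of dexamethasone, ending at least 24 hours before blinatumomab.

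- A 5-day course ending 24 hours before treatment starts 5 + 1 = 6 days before treatment.
- 14-day window: 14 ≥ 6, so a baseline can precede the whole course.
- Ordinary 7-day window: 7 ≥ 6, so it can there too. The extension makes an early draw easier but is not the sole cause.
- One trigger is a marrow blast count above 50%, which needs a marrow first. That makes a baseline before pre-phase likely, as well as possible.

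**2. What does the contrast contain?** On the log scale, for a patient with pre-phase:

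log(day 8-11) − log(screening) = [log(pre-infusion) − log(screening)] + [log(day 8-11) − log(pre-infusion)]

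The first bracket holds the pre-phase effect; the second holds day 1 dexamethasone premedication plus blinatumomab. Section 13.8.1 estimates the sum. Without pre-phase, the first bracket is 1-7 days with no pre-phase in between.

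**3. Is the day 1 sample a clean pre-infusion value?** Not as the windows stand.

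- At −3 or −2 days it can fall inside pre-phase, which need stop only 24 hours before infusion.
- At up to +3 days (Section 9.1, footnote 15) it follows premedication and the start of blinatumomab. Section 2.2.1.2.4 reports peripheral T cells falling to very low levels within 1 to 2 days and cytokines rising transiently in some subjects in the first 2 days.
- Appendix F rules out the late draw but not the early one.

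**4. Illustration of size.** Let f be the share of patients with pre-phase and r the fold change it causes. Neither is in the documents; both are assumptions. If the effect persists in full to the time point analysed, the pooled geometric mean ratio is multiplied by r^f:

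| f | r = 0.5 | r = 0.8 | r = 1.25 |
|---|---|---|---|
| 0.25 | 0.841 | 0.946 | 1.057 |
| 0.50 | 0.707 | 0.894 | 1.118 |
| 0.75 | 0.595 | 0.846 | 1.182 |

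With no persistence the factor is 1.00. The r = 1.25 column is there because direction is not known: Appendix C reports flow results as the percentage of gated cells that are positive, and a uniform fall in lymphocytes would leave such percentages unchanged.

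**The case against.** The strongest reply is that changing the reference can create bias as well as remove it. If the pre-phase effect has worn off by the time point analysed, the screening value is the better reference, and a day 1 reference would credit recovery to blinatumomab. That stands. A reader might infer that the bias sits at every later time point, but the documents give no persistence data. The argument is strongest for day 29 and the 3-12 month samples and weaker at day 8-11, where less time has passed.

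A reader might also infer that a clean post-pre-phase sample is already scheduled, so that rewording the SAP would suffice. The conflicting windows do not support this; used as they stand, they could build early drug effect into the reference, even in patients without pre-phase.

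Nor do the documents support replacing the reference in all change analyses. Section 9.2.3 schedules the TCR and transcriptome studies at pre-treatment, response and relapse. Comparing blood with marrow is a stated aim, which is why the baseline pair is taken together, and no day 1 marrow exists.

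Three further points stand in part. Flow is to be run at all Section 9.1 time points, so a day 8-11 versus day 1 contrast could be computed, but the plan does not specify it. Discretionary cytoreduction is not confined to high-burden patients, so the groups are not split cleanly by burden. And Section 13.8.1 calls these analyses descriptive and graphical, which limits what is at stake.

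**Conclusion.** The point holds for the run-in contrast. A baseline before pre-phase is permitted under both windows, the change model ignores pre-phase, and the day 8-11 change in these patients is pre-phase plus blinatumomab. Its size and sign cannot be calculated from the documents, and persistence to later samples is unknown. The table shows only what assumed values would imply, and applies to any marker only to the extent that pre-phase moves it.

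A stronger reading, that the CR and MRD comparisons are invalid and a new reference would repair them, is not supported. Burden itself may relate both to T-cell change and to response, and no choice of reference removes that. Even a clean day 1 reference measures blinatumomab together with the 20 mg dexamethasone premedication, though that is common to all patients.

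This is a minor, worthwhile correction. It touches exploratory endpoints only; safety, MTD and response results are unchanged.

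**What to change.** 1. Reconcile the cycle 1 day 1 research blood window across Section 9.1, calendar footnote 15 and Appendix F to one rule: drawn after pre-phase ends and before day 1 premedication and blinatumomab.
2. For peripheral blood flow and plasma cytokines (if measured), use that sample as the reference for the day 8-11 contrast. Report later time points against both the screening and the day 1 samples.
3. For marrow, and for the mixed models and CR/MRD interaction tests, include pre-phase (yes/no) or show the two groups separately. If the model is fitted to values rather than change scores, the term must be pre-phase by time point, since a main effect alone shifts level and not change.
4. Keep the screening sample for the baseline-predictor, TCR, transcriptome and paired blood-marrow analyses.

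Cost: no new specimen, but a small protocol clarification as well as SAP wording. The day 1 draw is smaller (30-40 cc against 60-100 cc), there are two blood references to report, and at least one more model term must be carried in at most 36 patients. Where that is too thin, the separate display is enough.
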